#### **5.1.2.5 Duration of Inhibition Response (Exploratory)**

Duration of inhibition response is defined as from baseline to either return to baseline or until Week 44, whichever comes first for inhibition responders. Participants who do not return to baseline will be censored at the time of study exit.

Duration of inhibition response will be summarized for each dose group, using Kaplan-Meier product-limit estimates.

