**Table 1. Objectives and Endpoints**

Objectives	Endpoints
Primary Safety and Tolerability	
To evaluate the safety and tolerability of UB-313, when administered at selected dose regimens given intramuscularly (IM) to healthy adults.	Safety will be assessed by adverse events (AEs), adverse events of special interest (AESIs), medically attended adverse events (MAAEs), local (injection site) and systemic (generalized) reactions (i.e., reactogenicity), clinical laboratory assessments (e.g., chemistry, hematology, urinalysis), vital signs, neurological and physical examinations and electrocardiograms (ECGs), through the end of study.
Primary Immunogenicity	
To evaluate the anti-Calcitonin Gene-Related Peptide (anti-CGRP) specific antibody responses to selected UB-313 dose regimens in healthy adults.	Immunogenicity will be measured serum anti-CGRP antibody titers and analyzed from baseline to Week 16 and Week 44.
Secondary	
To evaluate the effects of selected UB-313 dose regimens on capsaicin-induced dermal blood flow (DBF) as a surrogate marker of target engagement.	Pharmacodynamics (PD) of the immune response will be measured by the inhibition of capsaicin-induced increase in DBF and will be analyzed from baseline to Week 16 and until return to baseline or until Week 44, whichever comes first.
Exploratory	
To evaluate the effects of selected UB-313 dose regimens on CGRP concentrations in serum.	CGRP concentrations in serum through the end of study.
To characterize antibodies generated by UB-313.	Antibody titers against components of the UB-313 (i.e., CpG1 and UBITh1) through the end of study. Isotype-specific anti-CGRP antibody titers through the end of study.

To examine cytokine release induced by UB-313.	Cytokine release from peripheral blood mononuclear cell (PBMC)s stimulated with component of the UB-313 (T-cell ELISpot) through Week 16.
--	---

[figure not shown]

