### **4.0 General Consideration**

All analyses will be conducted using observed data only and no missing data will be imputed.

In general, the baseline value is defined as the last available value before the first injection of study dose.

All analysis and summary will be performed by dose group, defined as below:

- 100/100/100 $\mu$ g (8 active participants in cohort 1)
- 300/100/100 $\mu$ g (8 active participants in cohort 2)

- 300/300/300 $\mu$ g (8 active participants in cohort 3)
- 600/100/100 $\mu$ g (8 active participants in cohort 4)
- Placebo (8 participants from all cohorts)

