#### **5.1.2 Pharmacodynamics (PD) Analyses**

##### **5.1.2.1 Capsaicin Induced Dermal Blood Flow (Secondary Endpoint and Analysis)**

###### Capsaicin-induced increase in DBF (CIDBF)

The pharmacodynamics (PD) endpoint is the inhibition of capsaicin-induced increase in DBF (CIDBF). The DBF at each timepoint at each visit will be calculated as the average of two capsaicin-induced locations.

The DBF will be summarized for each timepoint (i.e., 0, 15, 30, 45, and 60 minutes) at each visit (i.e., Day 1, Day 29, Day 57, Day 85, Day 113, and Day 141, Day 197, Day 253, Day 309 as applicable).

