#### Change and Percent Change from Baseline (Day 1 prior to study IMP) in CIDBF

For 30 minutes and 45 minutes post capsaicin at each visit, change and percent change from baseline (Day 1 prior to study IMP) will be calculated. For example, change from baseline at 30 minutes post capsaicin on Day 29 is calculated as the DBF at 30 minutes post capsaicin on Day 29 minus the DBF at 30 minutes post capsaicin on Day 1 prior to study IMP. Percent change will be calculated similarly.

Summary will be presented. Between dose group comparison will be done. ANCOVA model will include dependent variable of change (or percent change) from baseline in CIDBF, with factor of dose group, and DBF at baseline (Day 1 prior to study IMP) as covariate.

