#### **5.1.2.4 Inhibition Responder (Exploratory)**

CIDBF at 30 minutes post capsaicin will be used for the responder analysis. To define threshold of response, mean and standard deviation will be calculated using the assessments below.

- CIDBF at baseline from all participants

The mean minus two standard deviations (mean-2SD) will be used as the threshold of response. CIDBF responders will be defined as the participants with CIDBF less than or equal to response threshold for each visit including baseline and postbaseline visits.

Responder analysis will be done similarly to seroconversion rates.

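### SAP 5.1.2.5 starts the duration of inhibition at the first dose rather than at response, and censors at study exit rather than at the last imaging visit (minor)

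*SAP*

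**What the plan says.** **Clock.** SAP 5.1.2.5 reads "Duration of inhibition response is defined as from baseline to either return to baseline or until Week 44", "whichever comes first for inhibition responders". SAP 4.0 says that "the baseline value is defined as the last available value before the first injection of study dose". For capsaicin-induced dermal blood flow (CIDBF), SAP 5.1.2.1 ties this to the first dosing day: "change and percent change from baseline (Day 1 prior to study IMP) will be calculated".

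**Response.** SAP 5.1.2.4 sets a threshold of mean minus 2 SD of the 30-minute baseline CIDBF from all participants. It then classes as responders those with CIDBF "less than or equal to response threshold for each visit including baseline and postbaseline visits". It names no onset date.

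**Censoring.** SAP 5.1.2.5 adds: "Participants who do not return to baseline will be censored at the time of study exit". Results are summarised by Kaplan-Meier for each dose group.

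**Imaging days.** SAP 5.1.2.1 lists "Day 1, Day 29, Day 57, Day 85, Day 113, and Day 141, Day 197, Day 253, Day 309 as applicable".

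**When imaging may stop.** The protocol synopsis (Capsaicin Challenge) and footnote 16 of the Schedule of Assessments allow laser speckle imaging (LSCI) to be dropped after Week 16. The condition is that the cohort's average response is back at baseline, judged by a ±2 SD rule on the cohort. SAP 2.2 keeps participants in the study to Week 44.

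**The concern.** The definition in 5.1.2.5 repeats almost word for word the window over which the pharmacodynamic endpoint is to be analysed. SAP Table 1 says the endpoint "will be analyzed from baseline to Week 16 and until return to baseline or until Week 44, whichever comes first", and the secondary endpoint in the protocol synopsis is similar. A window of analysis is not a duration. Used as one, it credits each responder with all the time between first dose and first response.

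The censoring rule is a separate matter. A participant whose imaging stopped early but who stays to Week 44 is counted as still inhibited for weeks in which nothing was measured. That sits badly with the rule in SAP 4.0 that only observed data are used and nothing is imputed.

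The protocol's Statistical Considerations give the second phase the aim of evaluating how the four regimens affect duration of response, and 5.1.2.5 is the SAP analysis with that name. A reader of the study report would take its median as the length of inhibition, which it is not.

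**Working it through.** The documents give no duration, so there is no planned figure to reproduce. The check is date arithmetic on nominal imaging days: 1, 29, 57, 85, 113, 141, 197, 253 and 309.

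**1. Clock.** Let O be the first responder visit and R the first later visit at which the participant is back at baseline.

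- Planned score = R − 1
- Visit-to-visit duration = R − O
- Difference = (R − 1) − (R − O) = O − 1

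For first response at Day 29, 57, 85 or 113, the plan therefore adds 28, 56, 84 or 112 days. Of these, 0, 28, 56 or 84 days run up to an earlier post-dose visit at which no response was seen.

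| Response seen from – gone at | Visit to visit | Planned score |
|---|---|---|
| Day 85 – Day 197 | 197 − 85 = 112 | 197 − 1 = 196 |
| Day 29 – Day 141 | 141 − 29 = 112 | 141 − 1 = 140 |
| Day 113 – Day 197 | 197 − 113 = 84 | 197 − 1 = 196 |

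The first two rows last equally long and score 56 days apart. The third is shorter than the second and scores 56 days more.

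The 112 days in the first row is itself a grid value. Onset lies between Days 57 and 85, and return between Days 141 and 197. The true duration is therefore between 141 − 85 = 56 and 197 − 57 = 140 days. The planned 196 lies outside that range.

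**2. Effect on a group median (invented group of 8).** First response is at Day 29 in 2, Day 57 in 3 and Day 85 in 3, and all return at Day 197.

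- Planned: 8 events at 196 days, median 196.
- From first response: 3 events at 112, 3 at 140 and 2 at 168. Survival falls to 5/8 = 0.625, then 2/8 = 0.25, then 0. Median 140.

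**3. Censoring.** Unmeasured time = exit day − last LSCI day, with exit at Day 309.

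- Last LSCI Day 141: 168 days = 24 weeks
- Last LSCI Day 197: 112 days = 16 weeks
- Last LSCI Day 253: 56 days = 8 weeks
- Imaged at Week 44 or at early termination: none

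**4. What censoring does to Kaplan-Meier (invented groups of 8, Day 1 clock).**

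- *Whole cohort stops at Day 141, 5 of 8 returned then.* Survival is 3/8 = 0.375 and the median 140 under both censoring rules. Under the plan, 3 participants stay at risk to day 308 on the clock; under last-LSCI censoring they leave at 140.
- *One participant not imaged after Day 113; events at 140, 196, 196, 252, 252, 308, 308.* Survival at 140, 196 and 252 is 0.875, 0.625 and 0.375 as planned, against 6/7 = 0.857, 4/7 = 0.571 and 2/7 = 0.286 with last-LSCI censoring. Median 252 under both.
- *Three participants not imaged after Day 113; events at 140, 196, 196, 252, 252.* Planned survival is 0.875, 0.625 and 0.375, median 252. With last-LSCI censoring it is 4/5 = 0.80, 2/5 = 0.40 and 0, median 196.

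A simultaneous cohort stop therefore changes only the tail and the late numbers at risk. The median can move only when last imaging dates differ within a group.

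**The case against.** **The clock is explicit and has merits.** Time from first dose has the same origin in every group and needs no onset date. That stands, and it is why renaming is an acceptable fix. It does not rescue the present label.

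**The ranking of regimens may not change.** Regimens that return on the same day tie under the planned clock, and nothing in the documents shows that onset differs by regimen. That stands: distorted rankings are possible, not demonstrated.

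**Censoring may hardly matter.** Stopping LSCI is optional, requires the cohort average to be back at baseline, and leaves the median alone if the group stops together. The one example with a shifted median needs 3 of 8 participants to stay in the study without imaging after Day 113, which nothing in the documents suggests. This too stands. The rule still credits unmeasured time.

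**Other analyses cover maintenance of effect.** Visit-level CIDBF summaries and ANCOVA, the AUC and the visit-level responder rates do not depend on 5.1.2.5. That limits the weight of the point.

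Two stronger readings are tempting and are not supported:

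- *A late responder could be scored 28 days.* A reader might infer that someone first responding at Day 85 has already returned at Day 29 (29 − 1 = 28), so that even the direction of bias is open. But a return presupposes a departure, and restricting the analysis to inhibition responders presupposes a response. On the ordinary reading the event follows the response. A clause saying so is worth adding; the 28-day score is not evidence of error.
- *The plan has no participant-level definition of return.* The SAP gives none, and the ±2 SD rule is for the cohort average. But only the protocol synopsis and schedule were available, so a definition in the protocol body cannot be excluded. This is a query.

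**Conclusion.** The point holds, at minor severity. As written, 5.1.2.5 yields time from first dose to loss of inhibition under the name of duration of inhibition. The excess is the onset day minus 1: 28 to 112 days for first responses between Day 29 and Day 113. Censoring at exit can add 8 to 24 unmeasured weeks for a non-returner whose imaging stopped between Day 141 and Day 253. That inflates the Kaplan-Meier tail and the late numbers at risk, and normally not the median.

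This rests on nominal visit days (windows reach ±14 days from Week 20), on reading the event as a return after response, and on exit at Day 309. The group examples are illustrations, not forecasts. The analysis is exploratory and descriptive, with at most 8 active participants per group. No primary or secondary conclusion changes.

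**What to change.** Amend SAP 5.1.2.5 as follows.

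- **(a) Censoring.** Censor non-returners at their last evaluable LSCI.
- **(b) Event.** State that an event is a return at a visit after the first post-baseline responder visit. State the participant-level return rule, or cite it if the protocol body has one. If the rule chosen is the first later visit above mean minus 2 SD, say that this changes the event from return to baseline.
- **(c) Clock.** Either start at the first post-baseline visit meeting the 5.1.2.4 threshold and report time to onset separately, or keep the Day 1 clock and rename the endpoint *time from first dose to loss of inhibition*.

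The cost is SAP wording and minor reprogramming, with no new data. Censoring at the last LSCI leaves fewer participants at risk late on. Moving the clock shortens the durations and makes onset interval-censored on a 4- to 8-week grid. It also exposes the start time to a single chance crossing of the threshold. How often that would happen depends on the distribution and between-visit correlation of CIDBF, which the documents do not give. A sensitivity analysis requiring two consecutive responder visits would guard against it but would drop genuine one-visit responders. Renaming avoids the noisy start but does not measure duration of inhibition.

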#### **5.1.3 Other Exploratory Analyses**

##### **5.1.3.1 CGRP Concentrations in Serum**

Summary will be done.

##### **5.1.3.2 Correlation between CIDBF, anti-CGRP Antibody, aCGRP Concentrations**

Correlation between CIDBF AUC (0 to 60 minutes) and anti-CGRP antibody at each visit will be summarized separately by dose group. Pearson's corelation coefficient will be calcaluated.

In addtion, correlation between CIDBF AUC (0 to 60 minutes) and aCGRP concentrations, aCGRP concentrations and anti-CGRP antibody at each visit will be done similarly.

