	
Cohort 3 may begin dosing at least 24 hours after all participants in Cohort 2 have received their first dose, and available (blinded) safety and tolerability data have been reviewed by the SRC. Based on the available data, a decision will be made to begin dosing of Cohort 3.
 
Participants will be provided with a diary. Starting the day of IMP administration, they will fill in the diary daily for 7 days, recording their temperature, and any solicited local and systemic symptoms of reactogenicity.
 
Capsaicin Challenge
 
A capsaicin-induced increase in DBF model will be used to assess the PDs of the UB-313-mediated immune response. Personnel who will perform these assessments will not be involved in UB-313 safety and tolerability evaluation due to the potential of unblinding. The capsaicin challenge will be conducted at Screening, Baseline before the first dose, and every 4 weeks up to Week 20 and subsequently every 8 weeks until the end of study at Week 44. After Week 16, LSCI assessment may no longer be required once the average capsaicin induced DBF increase within that cohort has returned to baseline (i.e., DBF response ± 2 SD before administration of IMP within a cohort).

Total Expected Number of Participants	Approximately 40 eligible healthy male and female participants (10 per cohort) will be enrolled to receive UB-313 or placebo.
Main Inclusion Criteria	
Full details of inclusion criteria are listed in the protocol. The main inclusion criteria include:
 
• Is a male or female aged 18 to 55 years old, inclusive, at time of informed consent.• Has a body mass index between 18 and 30 kg/m², inclusive at Screening, and with a minimum weight of 50 kg.• Male participants and their partners of childbearing potential must commit to the use of highly effective contraceptives for the study duration and for at least 12 weeks after the last dose. Men must refrain from donating sperm during this same period.• Female participants must be of nonchildbearing potential, or, for women of childbearing potential, must be willing to practice highly effective contraception throughout the duration of the study and for at least 24 weeks following the last dose.

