### **3.0 Analysis Sets**

The following populations sets will be used for the analyses.

- Full Analysis Set (FAS) consists of all participants randomized and received all three administrations of study Investigational Medicinal Product (IMP) per protocol, and who have at least one evaluable post baseline assessment of the anti-CGRP antibody titers.
- Safety Analysis Set (SS) consists of all participants who receive at least 1 dose of study IMP.

Demographic, baseline, and safety analysis will be based on Safety Analysis Set. Immunogenicity analyses, pharmacodynamics (PD) analyses, and exploratory analyses will be performed for FAS.

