#### **5.1.2.3 CIDBF AUC (Exploratory)**

CIDBF AUC (0-60min) and change from baseline (Day 1 prior to study IMP) will be summarized by dose group for each visit. Between dose group comparison will be done. ANCOVA model will include dependent variable of AUC, with factor of dose group, and baseline AUC as covariate.

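### The antibody–CIDBF correlation is planned only within dose groups of at most 8 and without reference to baseline AUC, so it is too imprecise to characterise a moderate relation

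*SAP*

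**What the plan says.** SAP section 5.1.3.2, under Other Exploratory Analyses, plans the following: "Correlation between CIDBF AUC (0 to 60 minutes) and anti-CGRP antibody at each visit will be summarized separately by dose group". On the measure it says "Pearson's corelation coefficient will be calcaluated". The pair of CIDBF AUC with aCGRP, and the pair of "aCGRP concentrations and anti-CGRP antibody at each visit will be done similarly", follow the same pattern.

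SAP section 4.0 fixes the groups: "8 active participants in cohort 1", the same number in each of cohorts 2 to 4, and "Placebo (8 participants from all cohorts" combined). These analyses use the Full Analysis Set, which takes only participants "randomized and received all three administrations of study Investigational Medicinal Product (IMP) per protocol" who also have a post-baseline titer. Missing values are not imputed. Eight is therefore a ceiling for each coefficient.

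Elsewhere the SAP does refer the AUC to baseline. Section 5.1.2.3 says "CIDBF AUC (0-60min) and change from baseline (Day 1 prior to study IMP) will be summarized by dose group for each visit", and its between-group ANCOVA carries baseline AUC as covariate. Section 5.1.3.2 uses neither device. It names no confidence interval, test or decision rule, and no section relates antibody to CIDBF across dose groups.

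**The concern.** Antibody titer is the primary immunogenicity measure, and CIDBF is the secondary measure, described as a surrogate of target engagement. Section 5.1.3.2 is the only planned analysis that sets one against the other participant by participant. It divides at most 40 people into five sets of at most 8 and never brings them together, so every estimate has the precision of a sample of 8 or fewer.

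It also leaves each person's own skin response in the AUC. That between-person variation can hide an antibody effect, and the baseline measurement that would remove it is already collected and already used in section 5.1.2.3.

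What is at stake is modest. The reader of the study report would have a long table of unstable coefficients, some with the wrong sign by chance, and no single estimate of how closely antibody and inhibition of flow go together.

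**Working it through.** **Inputs from the documents.** Four active groups of 8 and one placebo group of 8 (SAP 4.0): 4 × 8 + 8 = 40. This agrees with the Protocol synopsis: "Approximately 40 eligible healthy male and female participants (10 per cohort) will be enrolled to receive UB-313 or placebo". There are nine DBF visits, Day 1 and eight later ones as applicable (SAP 5.1.2.1). The documents give no target correlation, SD or power, so there is no stated figure to reproduce.

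**Inputs assumed.** Two-sided 5% level; Fisher z intervals; r = 0.5 as an example of a moderate relation. The expected sign is negative (more antibody, less flow). Sizes are shown as positive, and the intervals mirror.

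**1. Critical value.** |r| = t / √(df + t²).
- One group, n = 8, df = 6: 2.447 / √(6 + 5.988) = 0.71.
- 32 active participants adjusted for dose group, df = 27: 2.052 / √(27 + 4.210) = 0.37.
- Also adjusted for baseline AUC, df = 26: 2.056 / √(26 + 4.225) = 0.37.

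**2. 95% interval at r = 0.5.** tanh(atanh 0.5 ± 1.96 / √(n − 3 − k)), where k is the number of adjusting terms and atanh 0.5 = 0.549.
- n = 8, k = 0: 0.549 ± 0.877, giving -0.32 to 0.89. At r = 0 the interval is -0.70 to 0.70.
- n = 32, k = 4 (three dose-group terms and baseline AUC): 0.549 ± 0.392, giving 0.16 to 0.74.
- n = 32, k = 0 (unstratified pooling): 0.549 ± 0.364, giving 0.18 to 0.72.

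**3. Chance of detection and of a wrong sign.** Bivariate normal data; n = 8 simulated, dose-adjusted n = 32 (k = 3) by Fisher z approximation.

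| True \|r\| | Power, n = 8 | Wrong sign, n = 8 | Power, n = 32 dose-adjusted |
|---|---|---|---|
| 0.3 | 11% | 22% | 35% |
| 0.5 | 25% | 8% | 80% |
| 0.7 | 54% | 2% | 99% |
| 0.8 | 75% | under 1% | near 100% |

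**4. Baseline AUC: covariate or change score.** Let ρ be the test-retest correlation of AUC, which the documents do not give. Take post = ρ × baseline + β × titer + error, with titer independent of baseline, and scale AUC to unit variance at baseline and, apart from the titer effect, after it. A baseline-adjusted r of 0.5 means β² = [0.25 / 0.75] × (1 − ρ²). The correlation with the unadjusted AUC is then √[β² / (β² + 1)], and with the change score √[β² / (β² + (1 − ρ)² + 1 − ρ²)]. For ρ = 0.8, β² = 0.12, which gives √(0.12 / 1.12) = 0.33 and √(0.12 / 0.52) = 0.48.

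| ρ (assumed) | Unadjusted AUC | Change score | Baseline as covariate |
|---|---|---|---|
| 0.3 | 0.48 | 0.42 | 0.50 |
| 0.5 | 0.45 | 0.45 | 0.50 |
| 0.7 | 0.38 | 0.47 | 0.50 |
| 0.8 | 0.33 | 0.48 | 0.50 |
| 0.9 | 0.24 | 0.49 | 0.50 |

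The change score beats the unadjusted AUC only above ρ = 0.5. The covariate is at least as good as either at every ρ.

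**5. Stratify or pool.** Simulation under assumed values: titer rises of 3, 10, 10 and 30 fold; log10 SD 0.5; within-person CV 20%; between-person CV 25 to 40%; inhibition 15 to 30% per log10 titer. Combining the four by-group coefficients detected the relation in 13 to 68% of trials, and the dose-stratified analysis with baseline in 29 to 89%. When inhibition depended on regimen alone, with no titer relation inside a regimen, an unstratified pooled Spearman coefficient was significant in 10 to 27% of trials. The stratified version stayed near 5%.

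**The case against.** **The analysis is descriptive.** It is listed as exploratory, carries no test, and sits in a trial whose Protocol says that power was not considered. Neither the objectives nor SAP Table 1 names an antibody–PD relation. A reader might infer that the section is meant as an exposure-response analysis and fails at it; the documents do not give it that purpose. This stands, and it limits the importance of the point. It does not make an interval of -0.32 to 0.89 informative.

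**The coefficients are not useless.** A reader might infer that they cannot show any relation. That goes too far: power at n = 8 is about 75% when the true |r| is 0.8, and consistent signs over groups and visits would be descriptive evidence.

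**The four active coefficients can be combined.** By Fisher z the standard error is 1 / √(4 × 5) = 0.224, and at r = 0.5 the interval is 0.11 to 0.76. Much of the lost precision is thus recoverable from the planned output. But the SAP plans no such combination, and it would still leave baseline out. For the same reason it would be unfair to judge the plan by setting one coefficient from 8 people against an analysis of 32.

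**Skewness is partly dealt with.** Section 5.1 allows log transformation of titer and CIDBF if the distribution looks log-normal, and section 6.0 promises outlier sensitivity analyses. The rule is conditional, and section 5.1.3.2 does not say which scale the correlation uses. That is a gap in wording, not proof that untransformed titers will be used.

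**The number of coefficients is easily overstated.** Nine visits × five groups = 45 for this pair, but that is an upper bound: it counts Day 1 and placebo, and imaging may stop after Week 16. At most 8 × 4 = 32 are post-baseline coefficients in active groups.

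**Analysis by dose group avoids confounding titer with regimen.** This stands, and it is why the added estimate should be stratified and not simply pooled.

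**Conclusion.** The point holds as one of precision and of unused baseline information. Each planned coefficient rests on at most 8 participants, with a 95% interval of -0.32 to 0.89 at r = 0.5 and a critical |r| of 0.71. One dose-stratified, baseline-adjusted estimate from the same data narrows the interval to about 0.16 to 0.74 and the critical value to 0.37.

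The precision figures need only the group sizes in the SAP, full attendance and approximate normality; missed visits widen both intervals. The gain from baseline adjustment depends on the test-retest correlation of AUC, which the documents do not give: it is small at 0.3 to 0.5 and large at 0.8 to 0.9. The detection rates in step 5 rest wholly on assumed values, and the conclusion does not need them.

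The primary and secondary analyses are unaffected. This is a worthwhile, low-priority improvement.

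**What to change.** In SAP section 5.1.3.2:

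- **Main exploratory estimate.** At each post-baseline visit, give one partial correlation between log titer (or ranks) and CIDBF AUC (0 to 60 minutes) over all UB-313 participants with data (up to 32). Adjust for dose group and for Day 1 baseline AUC as a covariate, not through a change score, and give a 95% confidence interval.
- **Secondary.** Give the unstratified pooled coefficient with its interval, and note that it mixes between-regimen and within-regimen association.
- **Descriptive only.** Keep the by-group coefficients as planned.
- **Scale.** State whether titers are log-transformed for the correlation, so that it does not hang on the conditional rule in section 5.1.

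No new data, visits or change in conduct are needed; the cost is a short paragraph and a few lines of code. The stratified estimate assumes a common relation within the active groups, which the by-group coefficients can only roughly check. It also does not use the titer spread between regimens, which is why the pooled coefficient is reported beside it.
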